There is no provision for influenza vaccination in pregnant women to be given as part of standard antenatal care. Wong and colleagues (14) conducted a randomised controlled trial (RCT) to promote maternal influenza vaccination with one-to-one education as the intervention and showed that the intervention could increase the uptake from 10% to 21.1%. Our team has previously developed an intervention package which was proved effective in increasing influenza vaccine uptake in young children aged from 6 months to 2 years from 13% to 38% (12). The intervention package included: (i) a concise information sheet about the risk of influenza and benefits of influenza vaccination; (ii) semi-completed forms to utilise the Government's subsidy; (iii) contact details of nearby VSS registered clinics that do not charge above the subsidy; and (iv) vaccination reminders. This proposed study will compare influenza vaccine uptake in three groups of pregnant women: (i) a group offered a multi-component intervention package to encourage uptake of influenza vaccine through the VSS; (ii) a group offered the same package and free influenza vaccination as part of routine antenatal care; and (iii), a control group receiving current standard care.

3. Hypotheses and objectives

Hypotheses:

The uptake of seasonal influenza vaccine in pregnant women can be improved by providing mothers with either a multi-component intervention package to encourage influenza vaccine through the VSS or to offer free influenza vaccine as part of routine antenatal care.

Aims:

- 1. To determine whether influenza vaccine uptake in pregnant women can be increased with a multiple component intervention package and with influenza vaccine offered as part of routine antenatal care at no charge
- 2. To improve mothers' knowledge of maternal influenza vaccination
- 3. To explore whether influenza vaccine uptake in children at approximately 1 year old would be increased with the intervention

4. Study design

This is a prospective RCT of two interventions designed to improve influenza vaccine uptake in pregnant women. The study will be conducted in compliance with Declaration of Heisinki, ICH-GCP and standard CONSORT 2010 statement (15).

Subjects

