As a token of appreciation, we will offer cash or supermarket coupons with equivalent value of HKD200 (USD26) to subjects on completion of the study by registered mail, in consonance with local experience and international practice. Upon receiving the incentive, participants will be asked to sign on a form of acknowledgement of receipt (attachment I). Dates of incentive sent and received and the return of the acknowledgement of receipt will be recorded on a study log sheet as a governance system which will adequately monitor the disbursement of incentives to ensure accountability and traceability.

Interventions

Control Group

Subjects in the control group will receive the standard information about the VSS that is available from the CHP through text message in smart phones (https://www.chp.gov.hk/en/features/46107.html) (attachment II: Sample of VSS leaflet in 2020/21).

Intervention Group 1

Subjects in the intervention group 1 will receive an intervention package through text messages containing the following:

1. the same standard information about the VSS by CHP (https://www.chp.gov.hk/en/features/46107.html) as the control-subjects; and

2. additional interventions which include: a concise information sheet designed by our research team specifically for this study including (i) highlight of the risks of influenza in pregnant women and infants and the benefits of influenza vaccination to them (attachment III: Draft of concise information for intervention group 1), (ii) a hyperlink to the forms required for the VSS, if necessary, with guidelines to complete (attachment IV: Sample of VSS consent 2001/2021), and (iii) a hyperlink of Department of Health (DH)'s website to search for VSS registered clinics that do not charge additional fees for influenza vaccination above the subsidy.

When vaccination is possible, they will receive text message reminders for vaccination (also contain the concise information sheet) with a further reminder one to two months later.

Intervention Group 2

Subjects in the intervention group 2 will receive the same standard information about the VSS by CHP (https://www.chp.gov.hk/en/features/46107.html) as the control-subjects and the same multiple interventions as the intervention group 1 through text message. In addition the subjects will be informed that should they prefer they can receive free influenza vaccine during future antenatal follow-up visit once the vaccine is available.

Methods

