A previous Hong Kong RCT showed that the influenza vaccine uptake in pregnant women was 4.3% in 2014-2015 (12). Three other local studies showed 3.9% in 2005/06 (10), 6.2% in 2009/10 (13) and 1.7% in 2010/11 (11). Following the COVID-19 pandemic we anticipate that there will be greater awareness and acceptance of influenza vaccines. In a local RCT to promote maternal influenza vaccine uptake conducted by Wong and colleagues in 2013-2015 (14), the uptakes in the control and intervention groups were 10% and 21.1% respectively. They reported that the higher-than-expected vaccination rate in the control group might indicate the study itself increased the knowledge or awareness of influenza vaccination in the control subjects. To ensure we will have enough sample to prove the hypothesis, we assume a baseline uptake of 10% in the sample size calculation. A similar intervention package was effective in increasing influenza vaccine uptake in children aged from 6 months to 2 years by 25 percentage points (12). We expect the improvement in uptake would be more difficult in pregnant women (conservatively around 20 percentage points increase). Because of the different settings and policies in the two study sites, analysis will be stratified by study sites. Based on a required power of 80% and a significance level of 0.05, by using G*Power (version 3.1.9.4), the sample size required in each group is 69, and thus 414 in total in two study sites. Taking into account participants who do not complete the study (about 20% from past experience), the sample size required is 522 in total and 261 in one study site.

6. Study tools

The intervention will include: (i) standard information about the VSS that is available from the CHP through text message in smart phones (same as that for the controls); (ii) key information including highlight of the risks of influenza in pregnant women and infants and the benefits of influenza vaccination to them, a hyperlink to the forms required for the VSS, if necessary, with guidelines to complete, and a hyperlink of DH's website to search for VSS registered clinics that do not charge additional fees for influenza vaccination above the subsidy; (iii) text message reminders for vaccination; (iv) and being

informed that should they prefer they can receive free influenza vaccine during future antenatal followup visit once the vaccine is available.

7. Safety

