Not applicable as this research does not involve any safety issue. Common side effects of influenza vaccination include soreness, redness and swelling where the vaccine was given, mild headache, fever, muscle aches and fatigue.

8. Statistics

Exposures

Intervention Group 1: Type of intervention given: (i) concise information, (ii) provision of and guidance on completing documentation to utilise vaccination subsidy, (iii) a hyperlink of DH's website to search for VSS registered clinics, and (iv) vaccination reminders.

Intervention Group 2: Access to free influenza vaccination at an antenatal clinic follow up visit.

Outcome measures

Primary Outcome measure Influenza vaccine uptake rate in pregnant women

Secondary Outcome measure

Knowledge and attitudes of mothers in relation to influenza disease and influenza vaccine before and after receiving intervention information

Statistical analysis

DMP Tool will be used to prepare a formal data management plan. To ensure data quality, data will be double-entered and validated using EpiData. Intention-to-treat analysis (20) will be used and any missing influenza vaccination status will be taken as no vaccination. Demographic and maternal health factors will be compared between intervention- and control-subjects. Wilcoxon rank-sum tests will be used for continuous variables and chi-square tests for categorical variables. Chi-square tests will be performed to examine the effectiveness of the intervention package in improving influenza vaccination uptake in pregnant women. Each HBM attitude statement will be scored from 1 to 4 (from strongly disagree to strongly agree). Cronbach's alpha (21) will be used to measure internal consistency of HBM constructs. Permutation tests (22) will be used to examine any paired difference in attitude scores before and after intervention delivery. All statistical analyses will be performed using statistical software R (version 3.6.1) and a two-tailed p-value < 0.05 will be taken as statistically significant.

9. Access to data

All personal information will be kept confidential and the use of the data collected will only be restricted in the office of the Department of Paediatrics of The Chinese University of Hong Kong. Access to data is only limited to authorised members of research team under the direction of the principal investigator.

10. Quality control and quality assurance

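### The only test the protocol names for the secondary outcome is a paired before-after test, which cannot show that either intervention changed mothers' knowledge or attitudes (Aim 2)

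*Protocol*

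**What the plan says.** Protocol Section 3 gives Aim 2 as "To improve mothers' knowledge of maternal influenza vaccination". Section 8 defines the only secondary outcome as "Knowledge and attitudes of mothers in relation to influenza disease and influenza vaccine before and after receiving intervention information".

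Under Statistical analysis, Section 8 names one inferential test for that outcome: "Permutation tests (22) will be used to examine any paired difference in attitude scores before and after intervention delivery". Cronbach's alpha is also mentioned, but it measures the internal consistency of the Health Belief Model (HBM) constructs and compares nothing.

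The between-group tests in the same paragraph belong to other variables. The sentence "Demographic and maternal health factors will be compared between intervention- and control-subjects" is followed directly by "Wilcoxon rank-sum tests will be used for continuous variables and chi-square tests for categorical variables". The remaining one concerns the primary outcome: "Chi-square tests will be performed to examine the effectiveness of the intervention package in improving influenza vaccination uptake in pregnant women".

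Three other statements bear on the point. Section 4 (Interventions) says "Subjects in the control group will receive the standard information about the VSS". Section 4 (Data collection) has the same questions asked at enrolment and again three to four weeks after the expected date of delivery. Section 5 reports that, in an earlier local trial, the higher-than-expected control vaccination rate "might indicate the study itself increased the knowledge or awareness of influenza vaccination in the control subjects".

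**The concern.** The trial randomises women to three arms so that change from other causes can be subtracted out. The paired test does not use that design. It asks whether a woman's score at follow-up differs from her own score at enrolment. The answer mixes any effect of the package with repeat questioning, an intervening influenza season, the experience of delivery, and the information that controls also receive.

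A significant result would therefore look the same whether the package worked or every arm moved by the same amount. If it were reported against Aim 2, the trial would claim an educational effect without having tested for one.

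The test is also written for attitude scores, while Aim 2 names knowledge and the outcome names both.

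**Working it through.** **1. Which test serves which variable (Section 8)**

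| Variable | Named test | Contrast |
|---|---|---|
| Demographic and maternal health factors | Wilcoxon rank-sum, chi-square | between arms |
| Vaccine uptake (primary) | chi-square | between arms |
| Attitude scores (secondary) | permutation test | paired, within woman |
| Knowledge (secondary, Aim 2) | none named | none |

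**2. Inputs**

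- Completers: Section 5 requires 69 per group per site. The total is 69 × 3 × 2 = 414, and allowing for 20% loss gives 69 / 0.8 = 86.25, rounded up to 87, and 87 × 6 = 522. Both totals match the protocol. So there are 2 × 69 = 138 completers per arm over both sites.
- Significance level: two-sided 0.05 (Section 8).
- Not in the protocol: any expected shift in scores, any SD, any pre-post correlation, or any sample size for this outcome. The shift s (in SDs of the score) and the correlation r below are assumptions, shown over a range.

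**3. How often the paired test is significant when no intervention effect exists**

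Let all arms shift by s. The standardised within-woman change is d = s / √(2(1 − r)), and the noncentrality of a paired t-test, which approximates the paired permutation test, is d√n.

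Worked case, s = 0.25 and r = 0.5: d = 0.25 / √1 = 0.25.

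- n = 138: 0.25 × √138 = 2.94, giving 83.1%.
- n = 69 (one arm at one site): 0.25 × √69 = 2.08, giving 53.5%.

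| Shared shift (SD) | r | n = 138 | n = 69 |
|---|---|---|---|
| 0.15 | 0.5 | 41.7% | 23.3% |
| 0.25 | 0.3 | 69.3% | 40.9% |
| 0.25 | 0.5 | 83.1% | 53.5% |
| 0.25 | 0.7 | 96.4% | 75.3% |
| 0.30 | 0.5 | 93.8% | 69.0% |

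**4. The between-arm test under the same conditions**

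A simulation used 1,000 trials, 499 permutations each, 138 per arm and the same shift in both arms. The shift is in SDs of the change score, which equal SDs of the score when r = 0.5.

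| Shared shift | Paired test, one arm | Between-arm test of change |
|---|---|---|
| 0 | 5.5% | 5.2% |
| 0.2 | 65.9% | 5.0% |
| 0.3 | 92.6% | 4.5% |

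**5. Is the between-arm analysis feasible?**

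The difference detectable with 80% power is (1.96 + 0.84) × √(2/n) SD.

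- n = 138 per arm: 2.80 × √(2/138) = 0.34 SD. Baseline adjustment at r = 0.5 multiplies this by √(1 − 0.25) = 0.87, giving about 0.29 SD.
- n = 69 per arm at one site: 2.80 × √(2/69) = 0.48 SD unadjusted.

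**The case against.** The strongest reply is that the protocol does not call the paired test the sole analysis, and that a statistical analysis plan, not shown here, could add a comparison between arms. The outcome is itself defined as before and after, so the test matches its definition, and nothing says that a significant result will be read as an intervention effect. This does not rescue the plan. The protocol does not leave the method open: it names a test, and that test cannot answer Aim 2. Running it separately in each arm would not help, because significance in one arm and not in another is not a test of the difference.

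Several narrower points do stand.

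- The percentages rest on assumed shifts and correlations. The earlier trial's remark makes a shared rise plausible but does not measure one.
- If scores truly rise, rejecting no change is correct. The 83% is the power to detect a shared rise, and becomes a false-positive rate only when the result is taken as evidence for the intervention.
- Section 5 says that analysis is stratified by site, so the 69-per-arm column may be the relevant one.
- Attitude scores may be loose wording for the whole HBM-based questionnaire, which Section 4 says assesses knowledge and attitudes together. The text does not settle this.
- The primary outcome, its chi-square test and the sample size are untouched.

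**Conclusion.** The concern holds. The protocol fixes a within-woman test as the only named inferential analysis of its sole secondary outcome, and that test makes no use of randomisation. This conclusion follows from the text and depends on no assumed value.

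The size is illustrative. With a correlation of 0.5, no intervention effect and a rise of 0.15 to 0.30 SD shared by all arms, the paired test is significant in 42% to 94% of trials at 138 completers per arm, and in 23% to 69% at 69 per arm. A between-arm comparison stays at about 5%. This must be corrected before any result is reported against Aim 2.

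**What to change.** Replace the paired-test sentence in Section 8 with a between-arm analysis.

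- Compare the follow-up knowledge score and the follow-up HBM construct scores between each intervention arm and control, adjusted for baseline score and site. Analysis of covariance would do, as would a permutation test that permutes arm labels within site.
- Report each between-arm difference with a 95% confidence interval.
- Name knowledge explicitly and say how it is scored. Section 8 defines scoring only for the attitude statements (1 to 4), so also say how these combine into construct scores.
- Reword the secondary outcome as a difference between arms, and keep within-arm change as description without a claim of effect.

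The cost is wording in Section 8 or in the statistical analysis plan. Both questionnaires are already planned for all arms, so no extra data or participants are needed.

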All participants will be followed up first by text message at three to four weeks after their expected date of delivery by research staff who will be blinded to treatment group allocation. After confirming delivery, an online self-administered questionnaire will be completed by the participants. If the participants cannot complete the questionnaires online, hardcopy of the questionnaires with stamped and addressed return envelopes will be sent to their home. Follow-up by phone will be the last resort. Attachment VII shows the logistic flow of the proposed study. Participants who agree to be followed up at children's age of approximately 1 year will receive text messages around the time for vaccination information.

Data collection

Data will be collected at two to three time-points: at enrolment and at three to four weeks after the expected date of delivery; and optionally at children's approximately 1 year old. All questionnaires will be self-administered (attachment VIII). The following information will be collected at each time point:

- 1. At enrolment
 - Demographic information
 - Age/ year of birth, place of birth, highest educational level attained, occupation, marital status, household members and income, cigarettes and alcohol consumptions, and receiving CSSA or not
 - Personal identifies such as contact numbers, postal and residential address will be recorded in a separate logbook and linked only to the study number
 - Maternal health information
 - Expected date of delivery, gravidity and parity, pregnancy related health problems, and disease history (17)
 - Vaccination information
 - Heard of influenza vaccine, awareness of influenza vaccination recommendations in priority groups (pregnant women, persons aged 50 years or above, and children aged from 6 months and less than 12 years), and awareness and understanding of VSS in priority groups
 - Influenza vaccination history of mothers and family members in the same household
 - Vaccination status during this and previous pregnancies
 - Knowledge and attitudes in relation to influenza disease and influenza vaccine
- 2. At three to four weeks after the expected date of delivery
 - Influenza vaccination information during pregnancy
 - Vaccination status of mothers and family members in the same household
 - Reasons of receiving or not receiving influenza vaccine
 - Recommendations of receiving or not receiving influenza vaccine
 - Maternal health status during pregnancy

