 - Perceived health status during pregnancy, pregnancy related health problems, and respiratory illnesses and symptoms (17)
 - Infant's information
 - Sex, date of birth, gestational age, method of delivery, and birth weight
 - Caregiver and decision maker on infant's vaccination
 - Infant feeding intension or practice
 - Knowledge and attitudes in relation to influenza disease and influenza vaccine
 - Whether they read the information provided by the research team
 - Perception on change of behaviour because of the control/intervention packages

- 3. At approximately children's age of 1 year
 - Vaccination information of mothers and children
 - Influenza vaccination status of mothers
 - Any vaccination status of children
 - o Reasons of receiving or not receiving influenza vaccine
 - o Recommendations of receiving or not receiving influenza vaccine
 - Influenza infection history of mothers and children

Maternal knowledge and attitudes towards influenza and its vaccine will be assessed by a selfadministered questionnaire based on the Health Belief Model (HBM). The HBM is a simple, widely used framework to explain human health decision-making and behaviour (18;19). It contains six constructs to predict how humans make decisions, including perceived susceptibility and severity of illnesses, perceived benefits and barriers of interventions, cues to action and self-efficacy. The questionnaire will be based on the questionnaire from a previous study (12), and refined through further pilot testing. The same set of questions will be asked at the two data collection time-points.

5. Selection of subjects

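### Aim 2 names knowledge, but section 8 scores and tests only attitudes, before versus after, and the awareness and subsidy-scheme items are listed at enrolment only

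*Protocol*

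**What the plan says.** Protocol section 3 gives the second aim as "To improve mothers' knowledge of maternal influenza vaccination". Section 8 gives the secondary outcome as "Knowledge and attitudes of mothers in relation to influenza disease and influenza vaccine before and after receiving intervention information".

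Section 4, Data collection, has two separate relevant entries at enrolment. Under vaccination information it lists "Heard of influenza vaccine, awareness of influenza vaccination recommendations in priority groups", followed by awareness and understanding of the VSS. A later entry reads "Knowledge and attitudes in relation to influenza disease and influenza vaccine". The list for the questionnaire three to four weeks after the due date repeats that later entry but not the first. The optional list at about one year of age contains neither.

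The same section says that one self-completed questionnaire based on the HBM assesses both knowledge and attitudes, and that its questions are the same at the two time points. The model's constructs are given as "perceived susceptibility and severity of illnesses, perceived benefits and barriers of interventions, cues to action and self-efficacy".

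Section 8 rates each HBM attitude statement from 1 to 4 by strength of agreement and checks the internal consistency of the constructs with Cronbach's alpha. It then plans permutation tests that "will be used to examine any paired difference in attitude scores before and after intervention delivery".

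**The concern.** The aim and the analysis written for it do not match. Section 8 does more than leave the secondary outcome open. It fixes a scale, a reliability check and a test, and all three concern attitude statements or HBM constructs. Knowledge, the only thing Aim 2 names, receives none of them. Followed literally, the trial would report a change in attitudes under an aim about knowledge.

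Two further features make this more than a matter of wording. First, the listed items that ask most directly whether a woman knows of the recommendation and the subsidy are taken once, before any information is sent. Second, the stated test compares after with before. It does not use the randomisation, so it cannot separate what the package achieved from what would have happened anyway. The protocol itself gives reason for caution: section 5 reports that, in an earlier local trial of maternal vaccination, taking part may have raised knowledge or awareness among controls.

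**Working it through.** No figure is at stake. The protocol's only calculation is the sample size for vaccine uptake, which does not bear on this point. The check is a comparison of the collection lists with the analysis text.

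**Step 1. What is collected, scored and tested.**

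| Item | Enrolment list | Post-delivery list | Score in section 8 | Test in section 8 |
|---|---|---|---|---|
| Heard of the vaccine | yes | no | none | none |
| Aware of priority-group recommendations | yes | no | none | none |
| Aware of and understands the VSS | yes | no | none | none |
| Knowledge, in the questionnaire | yes | yes | none | none |
| Attitudes, in the questionnaire | yes | yes | 1 to 4 per HBM statement | paired, before versus after |

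Of the three awareness items, 3 of 3 are listed at enrolment and 0 of 3 after delivery. Of the two parts of the secondary outcome, one (attitudes) has a score and a test, and the other (knowledge) has neither.

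**Step 2. Could another follow-up entry cover the awareness items?** The post-delivery list has an entry on recommendations to receive or not receive the vaccine. It stands beside vaccination status and reasons for the decision, so it reads as advice the woman was given, not as her awareness of which groups are officially recommended. The repeated knowledge-and-attitudes entry does not obviously cover the items either, because at enrolment the protocol lists the two separately. The sentence about asking the same questions closes the paragraph on the HBM questionnaire and most naturally refers to that instrument.

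**Step 3. Could the HBM questionnaire supply a knowledge measure?** The six constructs are beliefs, cues and self-efficacy, and the only response format described is agreement, which has no stated correct answer. But the constructs describe the framework, not the item list. The protocol says that the questionnaire assesses knowledge too, and gives the 1-to-4 scale for HBM attitude statements without saying that every item is one. Factual items may therefore exist. The questionnaire is attachment VIII, which is not shown, so this stays open.

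**Step 4. What the paired test estimates.** Write the mean change in a package arm as b + d and in the control arm as b. Here b is the change that occurs without the package (from the standard VSS message sent to all three groups, the enrolment questionnaire itself, and the passage of time), and d is the effect of the package.

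- Before versus after in a package arm: b + d.
- Difference in change between a package arm and control: (b + d) − b = d.

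The stated test gives the first quantity. Only the second can be attributed to the package, and the randomised design already provides for it.

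**The case against.** A reader might infer that no change in knowledge can be shown at all and that Aim 2 has no usable endpoint. The documents do not support that. Knowledge and attitudes are listed at both time points, the questionnaire is said to assess both with the same questions, and section 8 names knowledge in the secondary outcome. Paired knowledge data are therefore planned, and the content of the questionnaire cannot be judged without attachment VIII.

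A reader might also infer that the awareness items are what the package teaches and so are the true knowledge measure. That goes too far as well. Standard VSS information goes to all three groups, controls included. What Groups 1 and 2 receive in addition is mainly a sheet on risk and benefit, help with the forms, a clinic-search link and reminders. Risk and benefit fall within the domain that is measured twice. The protocol places the awareness items with background vaccination information and does not designate them as the Aim 2 measure.

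The strongest remaining objection is that scoring and testing a secondary outcome is ordinary content for a statistical analysis plan, which may exist. That stands for the missing knowledge score taken alone. It does not stand for the collection gap, since no analysis plan can recover answers that were never requested. Nor does it cover the comparison: the protocol has chosen a test for this outcome and written it as before versus after.

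**Conclusion.** The point holds in a limited form. Aim 2 and the secondary outcome name knowledge, while the protocol's stated scoring and test cover attitudes only, and only as a paired difference. A change in the three awareness items cannot be measured in any arm from the listed data. A change in other knowledge may be measurable if the questionnaire holds factual items, but section 8 gives it no score and no test.

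This rests on two assumptions: that the lists in section 4 are complete as to what is asked at each time, and that the statement about identical questions refers to the HBM questionnaire. If attachment VIII already repeats the awareness items after delivery, the collection gap closes, and what remains is the mismatch between the aim and section 8 and the lack of a randomised comparison.

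Only a secondary aim is affected. The primary outcome, its analysis and the sample size are untouched. The change is still worth making because it is cheap and would let the trial attribute a change in knowledge to the package.

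**What to change.** 1. In section 4, add the three awareness items (heard of the vaccine, priority-group recommendations, awareness and understanding of the VSS) to the post-delivery list, worded as at enrolment.
2. In section 8, name a knowledge score made up of these items plus any factual items in the questionnaire, and state that it is the Aim 2 endpoint, separate from the HBM attitude scores.
3. In section 8, compare this score between the randomised groups with the enrolment value taken into account, for example by adjusting the follow-up score for it. The paired before-after difference can stay as description.

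The cost is a few existing items in a questionnaire already sent to every participant, an estimated one or two more minutes per respondent, and a few sentences of protocol text. The items can be added only for women who have not yet completed the post-delivery questionnaire, so this needs to be settled before that follow-up begins.
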